11.3 Other Adverse Events That Require Safety Analysis

Other adverse events that require safety analysis include AEs that fall under the “Embolic and Thrombotic Events” SMQ category and AEs with PT “Bone pain”.

Similar to AESI, summary will be provided for AEs that fall under the “Embolic and Thrombotic Events” SMQ category by preferred term. For “Bone pain” events, number of subjects with bone pain events by worst CTCAE grade will be provided from grade 1 to grade 3. The number and percentage of subjects with bone pain occurred during the first 24 weeks and after 24 weeks will be provided. Summary statistics will also be provided for time to first bone pain, total duration of bone pain (in days), total duration of bone pain that occurred during the first 24 weeks (in days), and total duration of bone pain that occurred after 24 weeks (in days). Total duration of bone pain is defined as sum of all bone pain duration within a subject, excluding overlapped period.

The “Embolic and Thrombotic Events” SMQ category analysis will include subgroup analysis by splenectomy status, platelet above ULN, concomitant medications, and comorbidities as needed.

11.4 Clinical Laboratory Evaluations

Clinical laboratory data is collected by central lab and local lab (if relevant to dose administration, modification and AE, or when no central lab results are obtained). Central laboratory assessments include hematology, chemistry, immunology, and pregnancy test. Local laboratory assessments include hematology, chemistry and urinalysis. Lab data will be collected over time during the study. All summaries will be based on the SI units and missing values will not be imputed. Clinical laboratory values will be graded (grade 0-4) according to NCI-CTCAE version 4.0 for applicable tests. Normal ranges will be used to determine the “High”, “Low”, and “Normal” categories for all numeric laboratory tests. Only central lab results and local lab “Reticulocyte (Blood)” parameter will be used for table summaries.

All clinical laboratory data during the Open-label Phase were collected by local lab only. Thus, the analyses of any clinical laboratory data for the Open-label Phase will be based on local lab data.

11.4.1 Hematology/Chemistry/Immunology

The laboratory results and change from baseline will be summarized by visit by treatment group for central lab hematology and chemistry panels separately.

A shift table representing the shift from the baseline grade to maximum NCI-CTC Grades (high or low) will be provided for selected hematology and chemistry parameters having toxicity grade by visit by treatment group. The shift summary for high category will be done for hepatic function parameter (ALT, AST, ALP, and total bilirubin) and renal function parameter (serum creatinine). The shift summary for low category will be done for hematology parameter (platelets, leukocytes and absolute neutrophil counts).

To estimate the incidence of subjects who have passed the predefined threshold for selected parameters, a summary table representing the number and percentage of subjects with lab assessments satisfying the threshold criteria will be provided by treatment group. A subject with post-baseline result (including “unscheduled” visits) meeting the criteria will be counted. The threshold criteria includes below:

LIVER FUNCTION	
Post-baseline Alanine Aminotransferase (ALT)	$\geq 3x$ upper limit of normal (ULN)
Post-baseline Aspartate Aminotransferase (AST)	$\geq 3x$ ULN
Post-baseline Direct Bilirubin (BILDIR)	$\geq 2x$ ULN

Post-baseline Total Bilirubin (BILTOTAL)	$\geq 2x$ ULN
Post-baseline ALT/AST and BILDIR	(ALT $\geq 3x$ ULN or AST $\geq 3x$ ULN) and BILDIR $\geq 2x$ ULN
Post-baseline ALT/AST and BIL TOTAL	(ALT $\geq 3x$ ULN or AST $\geq 3x$ ULN) and BIL TOTAL $\geq 2x$ ULN

RENAL FUNCTION	
Post-baseline Creatinine Clearance (CREATCLR)	< 0.5x baseline
Post-baseline Serum Creatinine (CREAT)	> 2x baseline
Albuminuria Category (ACR: mg/g)	<30
	≥30- ≤300
	>300-≤1000
	>1000-≤3500
	>3500
HEMATOLOGY	
Post-baseline Leukocytes (WBC)	≥ 2x baseline and > ULN
	≥ 3x baseline and > ULN
	≥ 2x baseline and > ULN and lasts for at least 42 days
	≥ 3x baseline and > ULN and lasts for at least 42 days
Maximum Post-baseline Platelets (PLAT)	≥ 1.5x baseline and > ULN
	≥600 - <1000x10 ⁹ /L

	$\geq 1000 \times 10^9/L$
--	---------------------------

Specifically, the threshold summary for platelets will be based on the maximum post-baseline value. The summary will be provided by baseline category based on normal range (i.e., within normal limit at baseline, > upper limit at baseline), and by splenectomy status (Yes, No) in separate tables. Furthermore, the number and percentage of subjects with maximum post- baseline WBC exceeding 3x baseline value and >ULN, maximum post-baseline WBC exceeding 3x baseline value and > ULN and lasts for at least 42 days, and subjects with maximum post- baseline platelets $\geq 600 - < 1000 \times 10^9/L$ and maximum post-baseline platelets exceeding $1000 \times 10^9/L$ will be provided separately by splenectomy status (Yes, No).

For some key lab parameters (ALT, AST, WBC), plots will be presented to show the pattern of the lab test values over time by treatment group. Mean and SE will be presented in the plot.

Listings of clinical laboratory data will be provided for central lab and local lab respectively for each panel (excluding serum erythropoietin and serum ferritin). Abnormal observations will be noted. Specifically, subjects with any WBC differential count exceeding 2x baseline value will be listed in a separate listing. All WBC differential count records of qualified subjects will be presented.

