 Vital signs (including heart rate, seated blood pressure [DBP and SBP], and temperature) will be measured at Screening, on Days 1 of each dose prior to administration of IP, at Treatment Discontinuation, at each visit during post-treatment Follow-Up, and at End of Study. Seated blood pressure should be confirmed by two separate measurements obtained predose and 10 minutes apart. The Investigator should report any clinically significant abnormal findings as adverse events.

 Pregnancy test is required for all female subjects of childbearing potential. Serum beta human chorionic gonadotropin (β-hCG pregnancy test (which must be negative) with a minimum sensitivity of 25 mIU/mL will be performed within 4 weeks prior Dose 1 Day 1. Urine (or serum) pregnancy test will be performed to assess subject eligibility within 72 hours prior to the first administration of IP, if the initial serum pregnancy test did not already occur with 72 hours of dosing (negative results required for IP administration). During the Treatment period urine or serum pregnancy test is allowed.

-  Hematology assessment includes RBC count, Hb, Hct, MCV, MCH, MCHC, RDW, WBC count with differential, absolute neutrophil count (ANC) and absolute lymphocytes, platelet and reticulocyte absolute values, and circulating erythroblast (nucleated RBC) counts. On dosing days, hemoglobin levels should be measured prior to dosing with IP to ensure Hb levels are within the acceptable ranges to allow luspatercept administration as per Section 7.2 and that luspatercept dose modification rules are followed as outlined in Table 5. Laboratory evaluations may be repeated more frequently if clinically indicated.
-  Serum chemistry (calcium, magnesium, phosphorus, blood urea nitrogen [BUN], creatinine, creatinine clearance, albumin, total protein, alkaline phosphatase, bilirubin [total, non-conjugated], AST/SGOT, ALT/SGPT, LDH and uric acid). If clinically significant, any or all laboratory evaluations should be reported as AEs and repeated more frequently, if clinically indicated.
-  For ADA test, additional blood draws are not needed. The test will be performed using the serum collected for PK samples. If ADA test is positive at the time of End of Study, the subject may need to return for additional ADA testing.
-  DXA scan of the lumbar spine and total hip for bone mineral density (BMD).

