- 12-lead electrocardiogram (ECG) - assessment should be performed within 4 weeks prior to Dose 1 Day 1 (read locally)
- Cardiac Doppler echocardiography, MUGA or MRI - left ventricular ejection fraction (LVEF)
- Pregnancy testing is required for all female subjects of childbearing potential. Serum beta human chorionic gonadotropin ( $\beta$ -hCG pregnancy test (which must be negative) with a minimum sensitivity of 25 mIU/mL will be performed within 4 weeks prior Dose 1 Day 1.
- For female subjects– menstrual status
- Hematology assessment includes a RBC count, Hb, Hct, mean corpuscular volume (MCV), mean corpuscular hemoglobin (MCH), mean corpuscular hemoglobin concentration (MCHC), red blood cell distribution width (RDW), white blood cell (WBC) count with differential, absolute neutrophil count (ANC), absolute lymphocytes, platelets, - central laboratory assessment should be performed within 4 weeks prior to Dose 1 Day 1. Absolute reticulocytes, and circulating erythroblasts (nucleated RBC) counts should be measured by local laboratory assessment within 4 weeks prior to Dose 1 Day 1
- Serum chemistry includes calcium, magnesium, phosphorus, blood urea nitrogen (BUN), creatinine, creatinine clearance, albumin, total protein, alkaline phosphatase, bilirubin (total, nonconjugated), aspartate aminotransferase (AST)/serum glutamic oxaloacetic transaminase (SGOT), ALT/ serum glutamic pyruvic transaminase (SGPT), lactic dehydrogenase (LDH) and uric acid - central laboratory assessment should be performed within 4 weeks prior to Dose 1 Day 1
- Urinalysis: microalbumin, creatinine, microalbumin/creatinine ratio (morning void; central lab) - central laboratory assessment should be performed within 4 weeks prior to Dose 1 Day 1
- MRI for LIC (T2\* or R2, mg/g dw). The same MRI technique should be used within a subject throughout the study duration.

- MRI or abdominal ultrasound for spleen measurement, unless splenectomized. If MRI is used: the spleen volume (cm^3) should be measured in the same acquisition as the MRI for LIC, if possible. If abdominal ultrasound is used for spleen measurement, the longest longitudinal dimension and width should be taken.
- MRI for myocardial iron (T2\*; ms)
- Bone mineral density by dual energy x-ray absorptiometry (DXA) scan - lumbar spine and total hip.
- QoL Questionnaire (TranQoL; SF36) - assessment should be performed within 4 weeks prior to Dose 1 Day 1
- HRU

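### The liver threshold table in SAP 11.4.1 mixes bilirubin elevations present at baseline with new ones, because its bilirubin and combined rows take no account of baseline

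*SAP*

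**What the plan says.** SAP section 11.4.1 introduces a table of laboratory thresholds as an estimate of the incidence of subjects who pass them. The counting rule is that a subject with a post-baseline result, unscheduled visits included, "meeting the criteria will be counted". The liver rows are:

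- ALT at or above 3x ULN, and AST at or above 3x ULN, each alone;
- "Post-baseline Direct Bilirubin (BILDIR" and "Post-baseline Total Bilirubin (BILTOTAL", each at or above 2x ULN;
- "Post-baseline ALT/AST and BILDIR", which requires ALT or AST at or above 3x ULN together with direct bilirubin at or above 2x ULN, and a matching row for total bilirubin.

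No liver row refers to the baseline value. In the same table the creatinine clearance, serum creatinine and WBC rows, and one platelet row, are multiples of baseline. For the platelet thresholds the SAP adds: "The summary will be provided by baseline category based on normal range".

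The same section also plans a shift table from baseline grade to maximum grade for ALT, AST, ALP and total bilirubin, and change from baseline by visit. SAP section 11 shows the original placebo subjects as a separate group.

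The protocol chemistry panel lists "bilirubin [total, non-conjugated" in the Table 3 footnote on serum chemistry and "bilirubin (total, nonconjugated" in section 6.1. Direct bilirubin is not listed, and the SAP gives neither a derivation nor a ULN for it.

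**The concern.** A row that estimates incidence should separate subjects who cross a limit on study from subjects who were over it already. Protocol section 1.1.2.1 names hemolysis among the disease mechanisms, so raised total bilirubin before dosing is to be expected in some subjects. Protocol section 4.3 excludes ALT above 3x ULN but sets no bilirubin limit; the general exclusions for laboratory abnormalities leave that to judgment.

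Two things follow. In the stand-alone total-bilirubin row, subjects with long-standing elevation count in both groups and pull the two percentages together. In the combined row, a subject who is already at or above 2x ULN bilirubin needs only one ALT or AST value at or above 3x ULN to be shown as a joint case. The joint rows are the part of the table that a safety reader is likely to look at first, and they would not show which cases are new in both components.

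**Working it through.** The plan states no figure for this table, so there is nothing to reproduce. The documents give no baseline bilirubin distribution and no expected liver event rates. The rates below are assumptions, used only to show direction and size.

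**Inputs**
- Group sizes: 200 luspatercept and 100 placebo (Protocol 9.3).
- b: share of subjects at or above 2x ULN total bilirubin at baseline who stay there. Assumed 0%, 10%, 30% or 50%, the same in both groups.
- r: rate of new elevation among subjects who start below 2x ULN. Assumed 2% on placebo and 10% on luspatercept, a true ratio of 5.0.

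**Stand-alone total-bilirubin row**

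Row rate = b + (1 − b) × r.
- b = 10%: placebo 0.10 + 0.90 × 0.02 = 11.8%; luspatercept 0.10 + 0.90 × 0.10 = 19.0%; ratio 1.61.
- b = 30%: placebo 0.30 + 0.70 × 0.02 = 31.4%; luspatercept 0.30 + 0.70 × 0.10 = 37.0%; ratio 1.18.

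As a gauge of lost contrast, the last two columns give the power of a two-sided 0.05 comparison of proportions. The SAP plans no such test for this row.

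| b | Placebo | Luspatercept | Ratio in row | Power, row as planned | Power, subjects below 2x ULN at baseline |
|---|---|---|---|---|---|
| 0% | 2.0% | 10.0% | 5.0 | 75% | 75% |
| 10% | 11.8% | 19.0% | 1.61 | 34% | 70% |
| 30% | 31.4% | 37.0% | 1.18 | 16% | 57% |
| 50% | 51.0% | 55.0% | 1.08 | 10% | 41% |

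Among subjects below 2x ULN at baseline the ratio stays 5.0 throughout. At b = 30% the luspatercept row would hold 200 × 0.37 = 74 subjects, of whom 200 × 0.30 = 60 were elevated at baseline and 200 × 0.70 × 0.10 = 14 are new. With new rates of 5% and 15% (true ratio 3.0), the row ratio is 1.62, 1.21 and 1.10 at b = 10%, 30% and 50%.

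**Combined ALT/AST-and-total-bilirubin row**

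Further assumptions: ALT or AST reaches 3x ULN in e = 2% (placebo) and 8% (luspatercept), independently of baseline bilirubin. Among those who start below 2x ULN bilirubin, q = 10% also have a bilirubin rise.

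Counted = e × [b + (1 − b) × q]. New in both components = e × (1 − b) × q. At b = 30%:
- placebo: 0.02 × (0.30 + 0.07) = 0.74% counted, against 0.02 × 0.07 = 0.14% new in both;
- luspatercept: 0.08 × 0.37 = 2.96% counted, against 0.08 × 0.07 = 0.56% new in both.

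The row shows about 6 luspatercept subjects (200 × 0.0296 = 5.92) where about 1 (200 × 0.0056 = 1.12) is new in both. The ratio between groups is 4 either way, because b and q are taken to be equal in the two groups.

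**Direct bilirubin**

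The listed panel gives total and non-conjugated bilirubin, so direct = total − non-conjugated. The rows can be computed from listed tests. What is missing is the statement that this is how the value is obtained, and the ULN against which 2x is judged.

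**The case against.** The strongest reply is that the liver evidence does not rest on these rows. ALT and AST have rows of their own that do not use bilirubin. Total bilirubin is related to baseline grade in the shift table of the same section, and chemistry changes from baseline are summarized by visit. The placebo group carries the same disease background. A high baseline bilirubin alone never puts a subject in the combined row. The table is descriptive, and liver injury is not among the adverse events of special interest in SAP section 11.2.

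Most of this stands, and it limits the point. It does not remove it. The shift table and the change-from-baseline summaries take one parameter at a time, so they do not identify joint cases. The placebo column shows the background, but it neither restores a diluted ratio nor separates old from new within a row.

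A reader might go further and infer that the direct-bilirubin rows will be empty and falsely reassuring because the protocol does not measure that fraction. The documents do not support this: the fraction follows from the two that are listed. A reader might also infer that the table cannot show a drug-related liver signal. The ALT and AST rows, the shift table and the placebo group contradict that.

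**Conclusion.** The table is meant to estimate incidence, but its total-bilirubin row counts prevalent and new elevations together. For subjects already at or above 2x ULN, the combined total-bilirubin row becomes an ALT/AST row. In the stand-alone row the effect is dilution: a true ratio of 5.0 would appear as 1.61 with 10% of subjects at or above 2x ULN at baseline, and as 1.18 with 30%. In the combined row the effect is over-counting of joint cases, with the ratio between groups roughly kept.

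These sizes rest on assumed prevalence and event rates, on baseline elevations persisting, and on equal baseline prevalence in the two groups. Persistence could itself differ by group: Protocol sections 1.2.1.1 and 1.3.1 report lower bilirubin in mice given the murine ortholog. The direction of the effect comes from the counting rule; only its size depends on the assumed rates.

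The absence of a stated source for direct bilirubin is a minor definitional gap. The point as a whole concerns the clarity of a safety table and does not touch the primary analysis.

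**What to change.** Present each bilirubin row and each combined ALT/AST-plus-bilirubin row by baseline bilirubin category, below 2x ULN against at or above 2x ULN, using the fraction on which that row is based. The SAP already uses a split by baseline category for platelets.

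Splitting is better than counting only subjects below the criterion at baseline. That exclusion would drop from the bilirubin row anyone who starts high and worsens further. In the combined row it would change little: a subject with high bilirubin and normal ALT/AST at baseline does not meet the joint criterion at that point, and would still be counted after an ALT rise.

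Separately, state that direct bilirubin is total minus non-conjugated bilirubin from the same sample, and which ULN applies, or drop the two direct-bilirubin rows.

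The cost is a slightly larger table, a few lines of SAP text, and programming on data already collected. The table is described in the future tense, which SAP section 2 reserves for analyses to be updated in the final CSR.

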11.4.2 Serum Erythropoietin and Serum Ferritin

Serum erythropoietin and serum ferritin are collected from central laboratory. The summary of serum erythropoietin test results and change from baseline will be provided by visit by treatment group. The summary of serum Ferritin is described in Section 10.5.4 as a study endpoint. A plot will be presented to show the pattern of the serum erythropoietin test results over time by treatment group. Mean and SE will be presented in the plot.

A listing will be provided for both serum erythropoietin and serum ferritin.

11.4.3 Local lab “Reticulocyte (Blood)” parameter

The “Reticulocyte (Blood)” parameter is only collected at local lab. The summary of absolute reticulocyte count and change from baseline will be provided by visit and treatment group in the same way as other lab parameters.

A line plot will be presented to show the pattern of the reticulocyte test results over time by treatment group. Mean and SE will be presented in the plot.

11.5 Vital Sign Measurements

Vital sign is collected over time during the study. Vital sign parameters include weight, temperature, pulse rate, seated blood pressure (diastolic blood pressure (DBP) and systolic blood pressure (SBP)). The DBP and SBP are collected twice at each visit with 10 minutes apart. The

average of the two assessments will be used. Summary statistics of observed values and change from baseline values will be presented for each parameter by visit by treatment group.

To further estimate the incidence of subjects whose maximum post-baseline blood pressure have passed selected criteria, summary tables representing the number and percentage of subjects with post-baseline (including 'unscheduled' visits) SBP/DBP assessments satisfying each criteria will be provided by treatment group. The selected criteria includes below:

Maximum post-baseline SBP	No increase
	Increased < 20 mmHg
	Increased \geq 20 mmHg
	Increased \geq 20 mmHg and SBP \geq 140 mmHg
	Increased \geq 20 mmHg and SBP \geq 150 mmHg
	Subjects only with baseline values
Maximum post-baseline DBP	No increase
	Increased < 20 mmHg
	Increased \geq 20 mmHg
	Increased \geq 20 mmHg and DBP \geq 100 mmHg
	Subjects only with baseline values

A plot will be presented to show the pattern of the SBP and DBP test results over time by treatment group. Mean and SE will be presented in the plot. Additionally, a spaghetti plot for SBP and DBP values overtime for individual subjects with maximum post-baseline SBP increased \geq 20 mmHg

and SBP \geq 150 mmHg or maximum post-baseline DBP increased \geq 20 mmHg and DBP \geq 100 mmHg will be provided.

Corresponding listing will be provided for vital sign data.

11.6 Electrocardiograms

The 12-lead electrocardiogram (ECG) is collected over time at selected visits. ECG parameters include heart rate, PR interval, QRS duration, RR interval and QT. The RR interval value will be derived per formula: RR interval (msec)=60000 (msec)/heart rate (bpm).

The corrected value for QT interval will be derived based on Fridericia's formula as below:

$$\text{Fridericia's formula: } QTcF = QT / (RR)^{1/3}$$

where RR is the calculated RR interval as above.

The calculated RR interval value, recorded values of other ECG parameters and change from baseline values will be summarized by visit by treatment group.

To further estimate the incidence of subjects whose baseline or post-baseline QTcF values have passed the selected ICH E14 Criteria, summary tables representing the number and percentage of subjects with ECG assessments satisfying the CPMP (Committee for Proprietary Medicinal Products) criteria will be provided for QTcF by treatment group and visit (for baseline and post-baseline respectively). A subject with baseline or any post-baseline (including 'unscheduled' visits) result meeting individual criteria will be counted. The selected CPMP criteria includes below:

Baseline/Post-baseline QTcF Interval	> 450 msec
	> 480 msec
	> 500 msec
QTcF Interval Increase from Baseline	\geq 30 msec
Post-baseline QTcF Interval and Increase from Baseline	Post-baseline Interval > 480 msec and Increase from Baseline \geq 60 msec

Corresponding listing will be provided for ECG data.

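### SAP Section 11.6 puts RR in milliseconds into the Fridericia formula, so every QTcF is ten times too small and the 450, 480 and 500 msec limits cannot be reached

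*SAP*

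**What the plan says.** SAP Section 11.6 (Electrocardiograms) lists the inputs: "ECG parameters include heart rate, PR interval, QRS duration, RR interval and QT". No unit is given for QT. RR is not taken from the tracing but derived from heart rate: "RR interval (msec)=60000 (msec)/heart rate (bpm"). The section then names the Fridericia correction and writes it as QT divided by the cube root of RR, with no division by 1000. It fixes which RR is meant: "where RR is the calculated RR interval as above".

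The resulting QTcF feeds a table of subjects meeting set criteria, by treatment group and visit:

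- an absolute value above 450, 480 or 500 msec, at baseline or after;
- "QTcF Interval Increase from Baseline" of at least 30 msec;
- a joint criterion, "Post-baseline Interval > 480 msec and Increase from Baseline" of at least 60 msec.

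The section is written in the future tense. SAP Section 2 says this marks analyses to be updated in the final CSR. SAP Section 11 says safety summaries use all collected records unless otherwise specified, including those after the primary database lock.

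**The concern.** The limits are in milliseconds on the ordinary QTc scale, where QTcF equals QT at 60 bpm. That holds only if RR enters the formula in seconds, so that RR = 1 at 60 bpm. With RR in milliseconds, RR = 1000 at 60 bpm and QTcF is a tenth of QT. The formula and the limits are therefore on different scales.

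This is the only analysis in the SAP that sets measured QTcF against limits, and the error runs in the reassuring direction. An empty table in every group would read as absence of QT prolongation, when the table could not have shown it.

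**Working it through.** **Inputs**

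- RR in msec = 60000 / heart rate (SAP 11.6).
- QTcF as written = QT / RR^(1/3), with that RR (SAP 11.6).
- Limits: 450, 480 and 500 msec; rise of at least 30 msec; above 480 msec with a rise of at least 60 msec (SAP 11.6).
- QT in msec. This is an assumption, because the SAP states no unit; it is the reading consistent with msec limits.
- The QT values of 400 and 500 msec and the heart rates below are illustrative.

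The documents report no QTcF result, so there is no figure of the plan's own to reproduce.

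**Step 1: the ratio.** With RR in seconds, QTcF = QT / (RR/1000)^(1/3) = QT × 1000^(1/3) / RR^(1/3) = 10 × QT / RR^(1/3). The value as written is therefore exactly one tenth of this, for every QT and every heart rate.

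**Step 2: examples.**

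| Heart rate (bpm) | RR (msec) | QT (msec) | QTcF as written | QTcF with RR in seconds |
|---|---|---|---|---|
| 60 | 1000 | 400 | 40.0 | 400.0 |
| 60 | 1000 | 500 | 50.0 | 500.0 |
| 75 | 800 | 400 | 43.1 | 430.9 |
| 100 | 600 | 400 | 47.4 | 474.3 |
| 120 | 500 | 400 | 50.4 | 504.0 |

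The last two rows show the consequence. At 100 bpm the subject is truly above 450 msec, and at 120 bpm above 500 msec. As written, neither comes near any limit.

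**Step 3: absolute limits.** To exceed 450, 480 or 500 as written, the true QTcF must exceed 4500, 4800 or 5000 msec. If QT cannot be longer than RR, the largest value the written formula can give is RR / RR^(1/3) = RR^(2/3). That is 100.0 at 60 bpm, 86.2 at 75 bpm and 71.1 at 100 bpm. Setting RR^(2/3) equal to the limit gives RR = limit^1.5:

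- 450: RR = 9546 msec, heart rate 60000/9546 = 6.3 bpm;
- 480: RR = 10516 msec, 5.7 bpm;
- 500: RR = 11180 msec, 5.4 bpm.

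Heart rate would have to be below these values. The three absolute limits cannot be met, and neither can the joint criterion, which includes the 480 limit.

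**Step 4: change from baseline.** Changes shrink by the same factor. A rise of 30 as written is a true QTcF rise of 300 msec. At a constant 60 bpm, QT would have to go from, say, 400 to 700 msec. At a constant 75 bpm the QT rise needed is 30 × 800^(1/3) = 278.5 msec, and at 100 bpm it is 30 × 600^(1/3) = 253.0 msec. This criterion is not ruled out by arithmetic, but in practice nobody would meet it.

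**The case against.** The strongest reply is that the effect depends on code the documents do not show. The SAP names a standard correction and gives limits on the standard scale, so the intent is clear and a programmer who knows the method would use seconds. A literal program would give values near 40 msec, which look absurd beside a QT near 400. The output is descriptive and carries no hypothesis test. ECGs are few: Table 3 of the protocol has them at screening, Dose 6, the first open-label dose for placebo or discontinued subjects, and treatment discontinuation. QT prolongation could also surface elsewhere, through the table of QTc prolongation adverse events in SAP Section 11.1, the recorded QT values and the ECG listing.

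Much of this stands as mitigation. The finding concerns the written rule, not results known to be wrong. The primary CSR was produced under a separate SAP dated 19 June 2018, which is not among the documents, so nothing can be said about QTcF results already submitted.

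It does not rescue the text. The SAP is the specification against which code is validated, and a check against this section would confirm the wrong values. Detection by eye is not assured either. The by-visit summary covers the calculated RR and the recorded values of the other parameters. QTcF is derived, so on a literal reading no table of QTcF means is required where 40 msec would stand out. The adverse event table depends on investigator reporting and does not replace measured limits.

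**Conclusion.** The point holds. As specified, QTcF and its changes are too small by a factor of exactly 10, whatever the heart rate. The 450, 480 and 500 msec limits and the joint criterion cannot be met; the stand-alone 30 msec criterion would need a true rise of 300 msec. The expected number of flagged subjects is zero in every group, regardless of the data.

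This rests on two assumptions: that QT is held in milliseconds, and that the program follows the text. Only the derived QTcF and its criteria are affected. RR, QT and the other recorded ECG values are not, and no efficacy result depends on this. It should still be corrected before the final CSR tables are relied on, because a safety table that cannot flag anyone gives false reassurance.

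**What to change.** In SAP Section 11.6, write QTcF = QT/(RR/1000)^(1/3), with QT and RR both in msec, and state those units. Leave the msec limits as they are. Confirm that the final CSR program converts RR to seconds, and recompute any QTcF already held in the analysis data against the corrected formula. A simple test is that QTcF must equal QT at 60 bpm.

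The cost is one line of SAP text, at most one line of code, and one check of derived values. No new data are needed.
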